## Statistical Analysis Plan (SAP) - Phase 2 Segment

### Revision History

Version	Date	Revisions
0.1	16 November 2020	Initial draft
0.2	12 January 2021	Internal Review
0.3	15 March 2021	Sponsor request to split out Phase 2 from Phase 3 for clarity
1.0	9 April 2021	Final v1.0
1.1	06-DEC-2021	Revised draft to incorporate changes in protocol USA v2.0
1.2	05-JAN-2022	Revised draft to incorporate comments from Inovio: unblinding at Week 30
2.0	20-JAN-2022	Final v2.0

## List of Abbreviations

Abbreviation	Explanation
AE	Adverse Event
AESI	Adverse Event of Special Interest
ALT	alanine transaminase
AST	aspartate aminotransferase
ATC	Anatomical Therapeutic Chemical
BMI	Body Mass Index
BP	Blood Pressure
BUN	blood urea nitrogen
CBC	Complete Blood Count
CI	Confidence Interval
CONSORT	Consolidated Standards of Reporting Trials
COVID19	Corona Virus Disease
CPT	cell preparation tubes
CRF	Case Report Form
CSR	Clinical Study Report
DSMB	Data Safety and Monitoring Board
ECG	electrocardiogram
ELISpot	enzyme-linked immune absorbent spot
EOS	End of Study
EP	electroporation
GCP	Good Clinical Practice
GMFR	Geometric Mean Fold Rise
H0	null hypothesis
H1	alternative hypothesis
HCO3	bicarbonate
HIV	human immunodeficiency virus
ICF	informed consent form
ICH	International Council for Harmonisation
IFN	interferon
IP	Investigational Product
IRT	Interactive Response Technology
ITT	Intent-to-treat
K	Potassium
LDH	Lactate Dehydrogenase
MAAE	Medically Attended Adverse Events
MedDRA	Medical Dictionary for Regulatory Activities
mRNA	messenger Ribonucleic Acid
O2	Oxygen
PCR	Polymerase chain reaction
PO4	Phosphate
PP	Per Protocol
PT	Preferred Term
RT	reverse transcriptase
SAE	Serious Adverse Event
SAP	Statistical Analysis Plan
SARS	Severe Acute Respiratory Syndrome
SD	standard deviation
SI	International system of units
SOC	system organ class
TEAE	Treatment Emergent Adverse Event
TLF	Table Listing and Figure
WHO	World Health Organization

### 1 Introduction

The purpose of this Statistical Analysis Plan (SAP) is to provide detailed descriptions of the statistical methods, data derivations, and data displays for the study protocol COVID 19-311 version 2.0 USA "Phase 2/3 Randomized, Blinded, Placebo-Controlled Trial to Evaluate the Safety, Immunogenicity, and Efficacy of INO-4800, a Prophylactic Vaccine against COVID-19 Disease, Administered Intradermally Followed by Electroporation in Healthy Seronegative Adults at High Risk of SARS-CoV-2 Exposure" dated 08-OCT-2021 for the analysis of the Phase 2 portion of the trial. A subsequent SAP will be developed specific for the Phase 3 portion of the trial. The table of contents and templates for the Tables, Listings, and Figures (TLFs) will be produced in a separate document.

Any deviations from this SAP will be described and justified in the Clinical Study Report (CSR).

The preparation of this SAP has been based on International Conference on Harmonisation (ICH) E9 and Good Clinical Practice (GCP) guidelines.

All data analyses and generation of TLFs will be performed using SAS 9.4® or higher.

### 2 Study Objectives

#### 2.1 Primary objective

- Evaluate the cellular and humoral immune response to INO-4800 administered by ID injection followed immediately by EP.

#### 2.2 Secondary objectives

- Evaluate the safety and tolerability of INO-4800 administered by ID injection followed immediately by EP

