## Statistical Analysis Plan (SAP) - Phase 2 Segment

In the Phase 2 segment, approximately 400 subjects 18 years of age and older will be randomized at a 3:3:1:1 ratio across four dose groups (Table 1).

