### 2.6 Randomization and blinding

At each clinical site, subjects who are eligible to enter phase 2 segment will be randomized to one of four treatment arms (INO-4800 1.0 mg, one injection; INO-4800 2.0 mg, two injections; Placebo, one injection; Placebo, two injections) in a 3:3:1:1 ratio, respectively, via the Y'Prime interactive response technology (IRT) randomization system. Randomization in this study will follow a permuted block randomization method. No stratification will be conducted.

This segment of the trial is double-blinded within dose-level, and group level unblinded summaries and analyses of immunogenicity and safety will be produced once the Week 6 immunogenicity data and Week 8 phone call visit data are completed for all subjects in the Phase 2 segment, which will be presented to the sponsor for dose selection for the Phase 3 portion. Per study protocol USA v2.0, all subjects will be unblinded when all subjects have completed the Week 30 study visit after identification and approval of the study populations.

Emergency unblinding procedures during the trial may be taken if the knowledge of the product administered is essential for the medical management of the subject by the principal investigator. Unblinding will be conducted through the IRT system. Notification to sponsor and medical monitor will be made for each unblinding and a record will be kept at each study site for all unbroken treatment codes and the reason for the need to break the treatment assignment.

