### **4 Sample Size and Power**

The phase 2 segment of this trial was not powered to conduct any formal hypothesis testing.

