## 7 Statistical Methods

### 7.1 General statistical conventions

All statistical procedures will be completed using SAS version 9.4 or higher.

Unless otherwise stated, all statistical testing will be two-sided and will be performed using a significance (alpha) of 0.05. Two-sided 95% confidence intervals (CI) will be provided when relevant.

Continuous variables will be summarized using descriptive statistics, including number of subjects (n), mean, median, standard deviation (SD), minimum, and maximum. Means and medians will be rounded to one more

decimal place than what is reported in the data. Standard deviations will be rounded to two more decimal places than what is reported in the data.

For categorical variables, summaries will include counts of subjects and percentages. Percentages will be rounded to one decimal place.

For summary purposes, baseline is defined as the last measurement prior to the first treatment administration. All summaries will be presented by treatment group, unless otherwise specified.

All subject data, including those derived, will be presented in individual subject data listings. Unless otherwise stated, unscheduled visit results will be included in date/time chronological order, within patient listings. All listings will be sorted by investigational site, subject ID, date/time and visit. The treatment group as well as the patient's sex and age will be stated on each listing. Unless otherwise stated, data listings will be based on all subjects randomized (ITT Population).

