### 7.7 Safety analysis

This section describes the safety analyses that will be conducted including all data collected in subjects who drop out.

All definitions relative to safety endpoints are detailed in [Section 3](#).

Safety analyses will be conducted on the safety population and will be performed for all safety variables specified below. All safety data will be summarized by treatment group. The summaries/analyses will be stratified according to NP positive/negative status of the subjects, prior receipt of any non-study prophylactic COVID-19 vaccine of the subjects, and age group. Strata for age group are 18 – 50, 51+ and 65+ years at Dose 1. Strata for NP status are positive and negative at each time point. Strata for prior receipt of any non-study prophylactic COVID-19 vaccine are yes and no at each time point. Additionally, a composite stratification of NP positive or non-study vaccinated and NP negative and not non-study vaccinated will be utilized.

The safety analyses of changes from baseline to a specific time point in safety variables (e.g., laboratory parameters, vital signs, ECG) will include subjects from the safety population who have data available for both the baseline and the time point under considerations unless otherwise specified.

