## Statistical Analysis Plan (SAP) - Phase 2 Segment

---

AEs will be classified as pre-treatment or treatment emergent (TEAE) defined as follows:

- Pre-treatment: any AE that started before the first dose date of the study treatment
- TEAE: any AE that was newly developed at or after the first dose date of study treatment

Details for imputing missing or partial start dates of adverse events are described in [section 6.2](#).

AE summary tables will include the following:

- All TEAEs
- Related TEAEs (AE will be defined as related if causality is either probable, possible, or definite)
- TEAEs by maximum severity
- TEAEs leading to treatment discontinuation
- Serious TEAEs
- TEAEs leading to death

All AEs including injection-site reactions will be summarized among the Safety Population by frequency per treatment arm. These frequencies will be presented overall and separately by dose, and will depict overall, by system organ class and by preferred term, the percentage of subjects affected.

Where a subject has the same adverse event, based on preferred terminology, reported multiple times in the treatment period, the subject will only be counted once at the preferred terminology level in adverse event frequency tables.

Where a subject has multiple adverse events within the same system organ class in the treatment period, the subject will only be counted once at the system organ class level in adverse event frequency tables.

Adverse events by severity and separately by relationship will be summarized based on the most intense event during the treatment period and strongest relationship to study treatment, respectively.

The main summary of safety data will be based on events occurring within 30 days of any dose. For this summary, the frequency of preferred term events will be compared between study arms with risk differences and 95% confidence intervals, using the method of Miettinen and Nurminen. As this analysis will use many event categories, and produce many confidence intervals, caution should be exercised when interpreting these confidence intervals. Separate summaries will be based on events occurring within 7 days of any dose and regardless of when they occurred.

The following sample of SAS code will be used to construct confidence intervals of the risk difference with the method of Miettinen and Nurminen:

```
proc freq data = <DATASET>;
  tables armcd * <OUTCOME> / riskdiff(CL= MN);
```

---

```
weight <COUNT>;  
run;
```

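### Phase 2 safety is compared only arm by arm; a supplementary INO-4800 versus placebo contrast stratified by number of injections would use all 400 subjects at little cost

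*SAP*

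**What the plan says.** **Objective.** Phase 2 SAP section 2.2 sets the secondary objective as "Evaluate the safety and tolerability of INO-4800 administered by ID injection followed immediately by EP". Section 2.4 repeats it as the safety objective. Neither mentions a dose level.

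**Design.** Under section 2.5, "approximately 400 subjects 18 years of age and older will be randomized at a 3:3:1:1 ratio across four dose groups". Section 2.6 lists the arms as "INO-4800 1.0 mg, one injection; INO-4800 2.0 mg, two injections; Placebo, one injection; Placebo, two injections", and Table 1 gives them 150, 150, 50 and 50 subjects. Section 2.6 adds: "This segment of the trial is double-blinded within dose-level".

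**Analysis.** The general rule in section 7.1 is "All summaries will be presented by treatment group, unless otherwise specified". Section 7.7 says "All safety data will be summarized by treatment group". Its strata are NP status, non-study vaccination, age group and a composite of the first two. Number of injections is not among them. For the main safety summary, section 7.7.1 states that "the frequency of preferred term events will be compared between study arms with risk differences and 95% confidence intervals", by the Miettinen-Nurminen method. The sample code there uses the variable armcd without defining it. The only definition, in section 7.6, lists the four arms separately.

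**Power.** Section 4 states: "The phase 2 segment of this trial was not powered to conduct any formal hypothesis testing".

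**The concern.** The objective asks about a product, and the tables answer for one dose level at a time. The two dose levels were randomized together, each at 3:1 active to placebo and each with its own blinded placebo. They are in effect two strata of a single active-versus-placebo question, yet the plan never combines them.

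What is at stake is precision. With about 50 placebo recipients per comparison, the intervals in the main safety summary are wide, most of all for less common systemic events. An excess of similar size at both levels is split between two imprecise comparisons, and a reader who wants one overall estimate would have to combine them after the results are known.

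**Working it through.** **1. Arm sizes.** 400 × 3/8 = 150 and 400 × 1/8 = 50, which reproduces Table 1. One matched pair uses 150 + 50 = 200 subjects, and both pairs together use 300 + 100 = 400. The SAP states no Phase 2 power or precision figure, so there is none to reproduce.

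**2. Is a combined contrast planned elsewhere?** Section 7.7.1 also says that AE frequencies are shown in total and split by dose. That sentence describes per-arm frequencies. It recurs in section 5.4.1 of the Phase 3 SAP, where there is only one dose level, so it most naturally means first and second dose. Section 7.6 lets either active arm serve as reference, so 150 versus 150 is possible as well, but no two-arm contrast uses all 400 subjects.

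**3. Is combining valid?** The ratio is 3:1 at both injection numbers, so active and placebo have the same expected mix of one and two injections. Stratifying by number of injections keeps each active arm with its own blinded placebo.

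**4. Width when observed rates are equal** (Miettinen-Nurminen 95% limits, percentage points):

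| Event rate in every arm | 150 vs 50 | 300 vs 100 | Ratio |
|---|---|---|---|
| 2% | 12.8 | 7.9 | 1.62 |
| 4% | 15.2 | 9.9 | 1.53 |
| 10% | 20.4 | 14.0 | 1.45 |
| 20% | 25.8 | 18.2 | 1.42 |

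For the first row, 3/150 vs 1/50 gives −8.63 to 4.16, and 6/300 vs 2/100 gives −5.11 to 2.77.

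**5. Chance that the interval lies above 0.** The lower limit exceeds 0 when

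T = (p1 − p0) / √[p(1 − p)(1/n1 + 1/n0) · N/(N − 1)] > 1.96,

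where p1 and p0 are the observed rates on INO-4800 and placebo, p is the pooled observed rate and N = n1 + n0. The probability comes from exact binomial enumeration. The two pairs share no subjects, so P(at least one) = 1 − (1 − P)². At 10% vs 2% this is 1 − 0.543² = 0.705. The rates are assumptions and are equal at both levels:

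| INO-4800 vs placebo | One pair | At least one pair | Neither pair | Combined |
|---|---|---|---|---|
| 10% vs 2% | 0.457 | 0.705 | 0.295 | 0.832 |
| 8% vs 1% | 0.429 | 0.674 | 0.326 | 0.838 |
| 15% vs 5% | 0.473 | 0.722 | 0.278 | 0.815 |
| 6% vs 2% | 0.109 | 0.206 | 0.794 | 0.313 |

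The combined column treats the data as 300 vs 100. Simulating the score test stratified by number of injections gives the same values in the first three rows to within 0.001 (0.831, 0.838, 0.816).

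**6. Unequal rates at the two levels,** placebo 2%:

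| INO-4800 rates at the two levels | At least one pair | Combined |
|---|---|---|
| 6% and 10% | 52% | 61% |
| 4% and 10% | 46% | 47% |
| 2% and 10% (one level only) | 46% | 31% merged, 34% stratified |

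**7. Rarer events,** equal rates at both levels. The combined chance is 22% at 4% vs 1%, 7% at 3% vs 1% and 1% at 2% vs 0.5%. The benefit here is mainly a narrower interval. With no event on INO-4800, the two-sided 95% upper bound is 1 − 0.025^(1/n): 2.4% for n = 150 and 1.2% for n = 300.

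**The case against.** The strongest reply is that by-arm analysis suits the purpose of this segment. Phase 2 is declared unpowered, its Week 6 and Week 8 summaries exist for dose selection (sections 2.5 and 7.8), and section 7.7.1 itself warns about over-reading the many intervals. The primary objective also names INO-4800 without a dose and is analysed by arm, so the wording of the objective does not require a product-level estimate. At the design stage, the Phase 3 segment was the larger safety comparison. The table shells are a separate document and may hold a combined column. All of this stands against calling the plan wrong. It does not remove the case for a supplementary estimate: the SAP makes risk differences with 95% intervals its main safety comparison, and their precision matters without any formal test. The SAP does not prespecify a combined contrast, whatever the shells contain.

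Three stronger readings are tempting, and the documents support none of them:

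- A reader might infer that the safety objective goes unanswered. It is addressed: all four arms are analysed, with risk differences and intervals.
- A reader might infer that an excess present at both levels would usually be missed in both comparisons. At 10% vs 2%, 8% vs 1% and 15% vs 5%, both pairs miss it in only 28% to 33% of trials. The fair comparison at 10% vs 2% is therefore 70% against 83%, not 46% against 83%. Both pairs do usually miss a smaller excess such as 6% vs 2% (79%), but there the combined contrast also misses it in 69%.
- A reader might infer that combining would settle the question for SAEs and AESIs. At low rates even 300 vs 100 has little chance of showing an excess.

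The two-injection arm also receives twice the product and twice the electroporation, so equal rates at both levels is the assumption most favourable to combining.

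**Conclusion.** The point holds as a gap in precision and as a cheap improvement. The Phase 2 SAP addresses safety only by arm, and no section prespecifies a product-level contrast, although the allocation and blinding make a stratified one valid. If rates are equal at both levels, by-arm intervals are about 1.4 to 1.6 times as wide as combined ones. At 10% vs 2%, the chance of an interval above 0 rises from 70% (either pair) to 83%. The gain shrinks with a dose gradient, is nil at 4% and 10% vs 2%, and becomes a loss when only one level carries the excess. For that reason the combined estimate can supplement the by-arm results but not replace them.

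The size rests on two things outside the text: the event rates, which the SAP does not give, and the 150 versus 50 pairing, which is inferred from the arm sizes and the section 7.6 coding.

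**What to change.** In Phase 2 SAP section 7.7.1:

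- Add a supplementary INO-4800 versus placebo risk difference with 95% interval (about 300 vs 100) for systemic events by SOC and PT, SAEs and AESIs.
- Stratify it by number of injections (one or two), using the stratified Miettinen-Nurminen method, so that each active arm is compared with its own placebo.
- Keep all by-arm tables, for dose selection and for injection-site reactions, and state that the combined estimate is read beside them.
- Name the arm pairs to be compared and define armcd for the safety code.

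The cost is a few lines of SAP text and one extra set of table columns, with no new data. The downside is that the combined estimate averages over two dose levels and can dilute an excess confined to one of them. The retained by-arm tables cover that.

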#### 2.3 Exploratory objective

- Evaluate the expanded immunological profile of antibody response and T cell immune response

#### 2.4 Safety objective(s)

The safety objectives are included within the secondary objectives and include the following:

- Evaluate the safety and tolerability of INO-4800 administered by ID injection followed immediately by EP

#### 2.5 General study design

This is an operationally seamless Phase 2/3, randomized, placebo-controlled, multicenter trial to evaluate the safety, immunogenicity, and efficacy of INO-4800, administered by ID injection followed immediately by EP using the CELLECTRA® 2000 device, in a 2-dose regimen (Days 0 and 28) in adults who are at high risk of SARS-CoV-2 exposure.

## Statistical Analysis Plan (SAP) - Phase 2 Segment

In the Phase 2 segment, approximately 400 subjects 18 years of age and older will be randomized at a 3:3:1:1 ratio across four dose groups (Table 1).

**Table 1: Phase 2 Segment Dose Groups**

Study Group	Expected Number of Subjects	Dosing Days	Number of Injections + EP per Dosing Visit	INO-4800 (mg) per injection	INO-4800 (mg) per Dosing Visit	Total Dose (mg)
INO-4800	150	0, 28	1	1.0	1.0	2.0
INO-4800	150	0, 28	2 a	1.0	2.0	4.0
Placebo	50	0, 28	1	0	0	0
Placebo	50	0, 28	2 a	0	0	0
Total	400					

aINO-4800 or placebo will be injected ID followed immediately by EP in an acceptable location on two different limbs at each dosing visit.

Dose selection for evaluation of efficacy in the Phase 3 segment will be based on Week 6 immunogenicity data and Week 8 safety data from the Phase 2 segment. Group-level unblinded summaries and analyses of immunogenicity and safety will be produced once the Week 6 immunogenicity data and Week 8 phone call visit data are completed for all subjects in the Phase 2 segment.

The total study duration is 393 days from Screening to end of study.

For safety issues or evidence of poor efficacy, the DSMB could recommend stopping enrollment at any time; no formal interim analysis will be performed for this purpose.

### 2.6 Randomization and blinding

At each clinical site, subjects who are eligible to enter phase 2 segment will be randomized to one of four treatment arms (INO-4800 1.0 mg, one injection; INO-4800 2.0 mg, two injections; Placebo, one injection; Placebo, two injections) in a 3:3:1:1 ratio, respectively, via the Y'Prime interactive response technology (IRT) randomization system. Randomization in this study will follow a permuted block randomization method. No stratification will be conducted.

This segment of the trial is double-blinded within dose-level, and group level unblinded summaries and analyses of immunogenicity and safety will be produced once the Week 6 immunogenicity data and Week 8 phone call visit data are completed for all subjects in the Phase 2 segment, which will be presented to the sponsor for dose selection for the Phase 3 portion. Per study protocol USA v2.0, all subjects will be unblinded when all subjects have completed the Week 30 study visit after identification and approval of the study populations.

Emergency unblinding procedures during the trial may be taken if the knowledge of the product administered is essential for the medical management of the subject by the principal investigator. Unblinding will be conducted through the IRT system. Notification to sponsor and medical monitor will be made for each unblinding and a record will be kept at each study site for all unbroken treatment codes and the reason for the need to break the treatment assignment.

### 2.7 Study treatments and assessments

The maximum duration of study participation from initial dosing to end of follow-up period is 393 days. The screening period can precede this active participation period by 1 to 30 days, for a total maximum duration of up to 423 days.

The investigational products (IPs) are: INO-4800, formulated in sodium chloride and sodium citrate buffer, refrigerated, and Placebo [sterile saline sodium citrate buffer (SSC-0001)], refrigerated.

#### Dosing regimens in Phase 2 Segment

- Active Investigational Product: One or two 1.0mg ID injection(s) of INO-4800 (~0.1mL dose volume each) followed immediately by EP administered on Day 0 and Day 28 ( $\pm 3$  days)
- Placebo: One or two ID injection(s) of SSC-0001 (~0.1mL) followed immediately by EP administered on Day 0 and Day 28 ( $\pm 3$  days)

Once eligibility has been confirmed, the subject will be randomized to receive a treatment assignment (INO-4800 or placebo). Visit dates and windows must be calculated from Day 0, unless otherwise noted. All subjects will be followed until the Day 393 Visit. All subjects will be followed in accordance with assessments outlined in the protocol.

The sponsor will continuously monitor emerging results from ongoing trials. Any evidence will be assessed by the Data and Safety Monitoring Board (DSMB) who will advise regarding any safety concerns and will make recommendations regarding continued enrollment, safety pause and trial suspension. If the safety data is considered unfavorable during any safety review, the DSMB may recommend a trial pause or trial termination at which time further enrollment and administration of IP to subjects will be paused. The Sponsor will perform an investigation and consult with the DSMB and other experts, if needed, to determine whether to resume dosing of the remainder of the subjects. For further details, see the DSMB Charter.

The detailed descriptions of procedures and assessments to be conducted during the Phase 2 segment in this trial are summarized in Phase 2 Segment Schedule of Events in [Table 2](#) below.

